**Other Exclusions:**

15. Total C radioactivity measured in plasma exceeding 11 mBq/mL at "Screening".
16. Females who are breastfeeding.

17. History of alcohol abuse or binge drinking and/or any other illicit drug use or dependence within 6 months of Screening. Binge drinking is defined as a pattern of 5 (male) and 4 (female) or more alcoholic drinks in about 2 hours. As a general rule, alcohol intake should not exceed 14 units per week (1 unit = 8 ounces (240 mL) beer, 1 ounce (30 mL) of 40% spirit or 3 ounces (90 mL) of wine).
18. History of tobacco or nicotine use within 3 months prior to dosing, or a positive cotinine at screening or Day -1.
19. Blood donation (excluding plasma donations) of approximately 1 pint (500 mL) or more within 60 days prior to dosing.
20. History of sensitivity to heparin or heparin-induced thrombocytopenia.
21. Unwilling or unable to comply with the criteria in the [Lifestyle Considerations](#) section of this protocol.
22. Participants with a history of irregular bowel movements eg, less than 1 bowel movement per day, regular episodes of diarrhea or constipation, irritable bowel syndrome (IBS) or lactose intolerance.
23. Participants enrolled in a previous radionucleotide study or who have received radiotherapy within 12 months prior to screening or such that total radioactivity would exceed acceptable dosimetry (ie, occupational exposure of 5 rem per year).
24. Participants whose occupation requires exposure to radiation or monitoring of radiation exposure.
25. Investigator site staff or Pfizer employees directly involved in the conduct of the study, site staff otherwise supervised by the investigator, and their respective family members.
26. Previous exposure to PF-07304814.

### **5.3. Lifestyle Considerations**

The following guidelines are provided:

#### **5.3.1. Meals and Dietary Restrictions**

- Participants must abstain from all food and drink (except water) at least 4 hours prior to any safety laboratory evaluations and 10 hours prior to the collection of the predose PK sample.
- Water may be consumed without restriction. Noncaffeinated drinks (except grapefruit or grapefruit-related citrus fruit juices—see below) may be consumed with meals and the evening snack.

- Lunch will be provided approximately 4 hours after the start of infusion.
- Dinner will be provided approximately 9 to 10 hours after the start of infusion.
- An evening snack may be permitted.
- Participants will refrain from consuming red wine, grapefruit, or grapefruit-related citrus fruits (eg, Seville oranges or pomelos) from 7 days prior to the first dose of study intervention until collection of the final PK blood sample.
- While participants are confined, their total daily nutritional composition should be approximately 55% carbohydrate, 30% fat, and 15% protein. The daily caloric intake per participant should not exceed approximately 3200 kcal.
- To help assure regularity in bowel movements, nutritional composition should contain at least 15 g of fiber per 1000 kcal or fiber capsules containing the equivalent amount of fiber may be administered daily (beginning at least 8 hours after dosing).
- If an individual participant has not experienced a bowel movement within 36 hours of their previous bowel movement, fluid intake should be increased and administration of a mild laxative (eg, prune juice or a mild stool softener) should be implemented, with the goal to facilitate at least 1 daily bowel movement. The use of laxative should be recorded.
- Participants will be asked to abstain from indigestible materials, eg, corn, nuts, etc, for 2 days prior to dosing and for the duration of the study in order to facilitate fecal homogenization.

### **5.3.2. Caffeine, Alcohol, and Tobacco**

- Participants will abstain from caffeine-containing products for 24 hours prior to the start of dosing until collection of the final PK sample is collected.
- Participants will abstain from alcohol for 24 hours prior to admission to the CRU and continue abstaining from alcohol until collection of the final PK sample. Participants may undergo an alcohol breath test or urine alcohol test at the discretion of the investigator.
- Participants will abstain from the use of tobacco- or nicotine-containing products for 3 months prior to dosing and during confinement in the CRU.

### **5.3.3. Activity**

- Participants will abstain from strenuous exercise (eg, heavy lifting, weight training, calisthenics, aerobics) for at least 48 hours prior to each blood collection for clinical laboratory tests. Walking at a normal pace will be permitted;

### **5.3.4. Contraception**

The investigator or his or her designee, in consultation with the participant, will confirm that the participant has selected an appropriate method of contraception for the individual participant and his or her partner(s) from the permitted list of contraception methods (see [Appendix 4](#)) and will confirm that the participant has been instructed in its consistent and correct use. At time points indicated in the schedule of activities ([SoA](#)), the investigator or designee will inform the participant of the need to use highly effective contraception consistently and correctly and document the conversation and the participant's affirmation in the participant's chart (participants need to affirm their consistent and correct use of at least 1 of the selected methods of contraception) considering that their risk for pregnancy may have changed since the last visit. In addition, the investigator or designee will instruct the participant to call immediately if the selected contraception method is discontinued or if pregnancy is known or suspected in the participant or partner.

### **5.4. Screen Failures**

Screen failures are defined as participants who consent to participate in the clinical study but are not subsequently enrolled in the study. A minimal set of screen failure information is required to ensure transparent reporting of screen failure participants to meet the CONSORT publishing requirements and to respond to queries from regulatory authorities. Minimal information includes demography, screen failure details, eligibility criteria, and any SAE.

Screen failures are defined as participants who consent to participate in the clinical study but are not subsequently enrolled in the study. Screen failure data are collected and remain as source and are not reported on the CRF.

Individuals who do not meet the criteria for participation in this study (screen failure) may be rescreened.

## **6. STUDY INTERVENTION(S) AND CONCOMITANT THERAPY**

Study intervention is defined as any investigational intervention(s), marketed product(s), placebo, medical device(s), or study procedure(s) intended to be administered to a study participant according to the study protocol.

For the purposes of this protocol, study intervention refers to PF-07304814, administered as a single, 24-hour constant-rate, continuous IV infusion of 500 mg containing approximately 420 nCi [C] PF-07304814.

### **6.1. Study Intervention(s) Administered**

[C]PF-07304814 will be provided by Pfizer as bulk API and, where necessary, bulk excipients for the manufacture of the [C] labeled IV formulation. The final product composition, sourcing of components and/or excipients, and presentation will be detailed in a separate Technical Agreement (TA) for IV drug product.

### **6.1.1. Administration**

Participants will receive 500 mg PF-07304814 containing approximately 420 nCi [C] PF-07304814 starting at approximately 08:00 hour (plus or minus 2 hours), administered as a single, 24-hour constant-rate, continuous IV infusion. Administration of [C] PF-07304814 will be performed by qualified investigator site personnel (in accordance with local regulations and laws). Investigator site personnel will administer study intervention according to the site administration instructions (SAI).

### **6.2. Preparation, Handling, Storage, and Accountability**

1. The investigator or designee must confirm appropriate temperature conditions have been maintained during transit for all study interventions received and any discrepancies are reported and resolved before use of the study intervention.
2. Only participants enrolled in the study may receive study intervention and only authorized site staff may supply or administer study intervention. All study interventions must be stored in a secure, environmentally controlled, and monitored (manual or automated recording) area in accordance with the labeled storage conditions with access limited to the investigator and authorized site staff. At a minimum, daily minimum and maximum temperatures for all site storage locations must be documented and available upon request. Data for nonworking days must indicate the minimum and maximum temperatures since previously documented for all site storage locations upon return to business.
3. Any excursions from the study intervention label storage conditions should be reported to Pfizer upon discovery along with any actions taken. The site should actively pursue options for returning the study intervention to the storage conditions described in the labeling, as soon as possible. Once an excursion is identified, the study intervention must be quarantined and not used until Pfizer provides permission to use the study intervention. Specific details regarding the definition of an excursion and information the site should report for each excursion will be provided to the site in a separate TA.
4. Any storage conditions stated in the SRSD will be superseded by the storage conditions stated on the label.
5. Study interventions should be stored in their original containers.
6. The investigator, institution, or the head of the medical institution (where applicable) is responsible for study intervention accountability, reconciliation, and record maintenance (ie, receipt, reconciliation, and final disposition records), such as the IPAL or sponsor-approved equivalent. All study interventions will be accounted for using a study intervention accountability form/record.

7. Further guidance and information for the final disposition of unused study interventions are provided in the TA. All destruction must be adequately documented. If destruction is authorized to take place at the investigator site, the investigator must ensure that the materials are destroyed in compliance with applicable environmental regulations, institutional policy, and any special instructions provided by Pfizer.

Upon identification of a product complaint, notify the sponsor within 1 business day of discovery.

### **6.2.1. Preparation and Dispensing**

Within this protocol, preparation refers to the investigator site activities performed to make the study intervention ready for administration or dispensing to the participant by qualified staff. Dispensing is defined as the provision of study intervention, concomitant treatments, and accompanying information by qualified staff member(s) to a healthcare provider, participant in accordance with this protocol. Local health authority regulations or investigator site guidelines may use alternative terms for these activities.

[C]PF-07304814 solution for the IV administration will be manufactured at the clinical study site by 2 trained personnel and quality assurance (QA) released prior to administration. Details of the dose preparation will be provided in a separate TA. Prepared doses will be provided in unit dose containers and labeled in accordance with Pfizer regulations and the investigator site's labeling requirements. Leftover containers following IV administration, including tubing used for infusion, should be shipped to laboratory for assessment of radioactivity, if needed.

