## 3. OBJECTIVES AND ENDPOINTS

Objectives	Endpoints
Primary:	Primary:

To confirm mass balance and characterize the routes of elimination of [C]-PF-07304814 and drug related materials following 420 nCi/500 mg dose of [C] PF-07304814

To evaluate the PK of PF-07304814 and PF-00835231 in plasma and characterize the PK of total [C] in plasma

	

Amount of [C] recovered in urine and feces, as a percent of the total [C] dose administered

Plasma PK parameters, including AUClast, AUCinf, Cmax, Tmax, C24, CL, Vss, and t1/2

Total [C] in plasma and PK of PF-07304814 and PF-00835231 in plasma

Secondary Objective:	Secondary:

To identify metabolites of PF-07304814 in plasma, urine and feces, if possible

To evaluate the safety and tolerability of a single, 24-hour constant-rate, continuous infusion of 500 mg PF-07304814 containing 420 nCi [C]-PF-07304814 in healthy participants

	

Identification and determination of relative abundance of the metabolites of PF-07304814 in plasma, urine, and feces

Assessment of TEAEs, clinical laboratory abnormalities, vital signs, physical exam, and 12-lead ECGs.

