## **6.4. Study Intervention Compliance**

When participants are dosed at the site, they will receive study intervention directly from the investigator or designee, under medical supervision. The date and time of each dose administered in the clinic will be recorded in the source documents and recorded in the CRF. The dose of study intervention and study participant identification will be confirmed at the time of dosing by a member of the study site staff other than the person administering the study intervention.

The site will complete a preparation record, which may be detailed in the TA. It does not preclude the use of an existing appropriate clinical site documentation system. The existing clinical site's documentation system should capture all pertinent/required information on the preparation and administration of the dose. This may be used in place of the Preparation Record after approval from the sponsor and/or designee.

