#### 9.3.1. Pharmacokinetic Analysis

##### 9.3.1.1. Mass Balance

Carbon-14 in urine will be measured using accelerator mass spectrometry and reported as the percentage of the administered dose of [C] excreted at each time interval and as the total percent of dose excreted in urine.

Carbon-14 in feces will be measured using accelerator mass spectrometry and reported as the percentage of the administered dose of [C] excreted at each time interval and as the total percent of dose excreted in feces.

Percent recovery of total [C] in urine and feces will be determined based on total administered dose.

Individual participant and median data profiles will be graphically presented for the cumulative recovery of [C] in urine, feces and their combination. The total recovery of [C] in urine, feces and their combination will be listed and summarized. Where possible the rate of excretion of [C] will be estimated.

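### Does the conditional assay of [14C] left in the container and tubing leave percent recovery, a primary endpoint, without a sound denominator?

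*Protocol*

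**What the plan says.** Protocol Section 3 gives the primary mass-balance endpoint as the [14C] "recovered in urine and feces, as a percent of the total" [14C] dose administered. Protocol 9.3.1.1 says that percent recovery of total [14C] "in urine and feces will be determined based on total administered dose", and SAP 6.3.1 repeats this. The urine table in Protocol 9.3.1.3 divides by a quantity called Dose_iv, described as the intravenously administered [14C] dose.

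On the dose itself, Protocol 6.1.1 says "Participants will receive 500 mg PF-07304814 containing approximately 420 nCi" of [14C] PF-07304814, infused at a constant rate over 24 hours. On what may be left behind, Protocol 6.2.1 says "Leftover containers following IV administration, including tubing used for infusion, should be shipped to laboratory for assessment of radioactivity, if needed". It gives no trigger. The same section leaves dose preparation to a separate technical agreement and requires quality-assurance release before use. Section 6.1.1 leaves administration to site instructions.

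The surrounding controls are general. Under Section 6.4, "The dose of study intervention and study participant identification will be confirmed at the time of dosing" by a second member of staff, and the site's documentation "should capture all pertinent/required information on the preparation and administration of the dose". Under Section 6.2, the investigator or institution "is responsible for study intervention accountability, reconciliation, and record maintenance". A later item of Section 6.2, on the disposition of unused product, contains the clause "If destruction is authorized to take place at the investigator site".

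**The concern.** A recovery percentage is only as good as its denominator. The plan guards the numerator closely: every void and bowel movement is collected, irregular bowel habit is an exclusion, and material soiled by diarrhea is kept. The denominator has no written derivation, and the one step that would measure undelivered [14C] is optional.

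The error would be one-sided. A residual cannot be negative, so using the prepared dose in place of the delivered dose can only lower recovery, and it does so in every participant. Summarizing 4 or 5 participants would not average it out. A shortfall of this kind would look like incomplete collection or retained drug. The second-person dose check takes place at dosing, before the 24-hour infusion has run, so it cannot show what stayed in the line. The same dose also enters clearance, steady-state volume and Ae%.

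**Working it through.** **Is there a figure to reproduce?** No. The plan gives no residual fraction, recovery target, power or precision figure. The check is a reading of both documents for any rule on the administered dose, followed by a sensitivity calculation.

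**Reading.** Protocol Section 3, Protocol 9.3.1.1, Protocol 9.3.1.3 and SAP 6.3.1 all point to the administered dose. No section names 420 nCi, or the amount prepared, as the denominator. No section says how the administered amount is obtained. The concern is therefore right that a derivation is missing. It would be wrong to infer that the nominal dose will be used.

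**Inputs.** Nominal [14C] dose: 420 nCi over 24 hours (Protocol 6.1.1). Residual fraction r: assumed at 2%, 5% and 10%, since the documents give none. True recovery: assumed at 90% and 95%.

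**Scale of the residual.** The infusion rate is 420 / 24 = 17.5 nCi per hour. The residual is 420 × r, and its equivalent in infusion time is r × 1440 minutes.

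**Effect on recovery.** If the full 420 nCi is wrongly used, reported recovery = true recovery × (1 − r). Example with r = 5% and true recovery 90%: delivered 420 − 21 = 399 nCi; recovered 0.90 × 399 = 359.1 nCi; 359.1 / 420 = 85.5%; 359.1 / 399 = 90.0%.

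| Assumed r | Residual (nCi) | Infusion time (min) | True 90% reads | True 95% reads |
|---|---|---|---|---|
| 2% | 8.4 | 28.8 | 88.2% | 93.1% |
| 5% | 21 | 72 | 85.5% | 90.25% |
| 10% | 42 | 144 | 81.0% | 85.5% |

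The word approximately in the dose statement works the same way, but in either direction. If the administered [14C] were 5% below or above 420 nCi (assumed), a true 90% would read 90 × 0.95 = 85.5% or 90 × 1.05 = 94.5% against the nominal figure. An approximate target is itself a reason to measure the dose.

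**What the denominator does not touch.** The share of recovered [14C] found in urine is U / (U + F), where U and F are the amounts in urine and feces. The dose cancels, so the relative routes of elimination are unaffected. Plasma total [14C] concentrations and half-life do not use the dose either.

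**Other parameters.** Ae% scales as (1 − r). A value of 10 becomes 9.8, 9.5 or 9.0, within the 9% to 11% seen in the earlier healthy-participant study (Protocol 2.2.4.2). Clearance and steady-state volume would be overstated by 1/(1 − r) − 1, which is 2.0%, 5.3% or 11.1%. Protocol Table 1 restricts both to the prodrug and to cases where data permit, and the prodrug half-life could not be determined in the earlier study. They may not be calculable at all.

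**The case for a change.** The strongest case for a change is that the denominator of a primary endpoint should be defined in the SAP, that the fix is small, and that discarded material cannot be assayed later. Part of this stands. Neither document derives Dose_iv, the assay has no trigger, and the arithmetic is correct.

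The rest is weaker. The site-destruction clause in Section 6.2 concerns unused product, is subject to authorization and follows the sponsor's special instructions. Used containers and tubing have their own sentence in Section 6.2.1, which sends them to the laboratory. The destruction argument therefore rests on text about other material.

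A large shortfall would also not pass unnoticed under the plan as written. A 10% residual equals 144 minutes of infusion. Protocol 8.3.10 treats an incorrect dosage as a medication error to be recorded on the CRF, the Mass Balance Analysis Set leaves out participants whose deviations may have affected the result, and SAP 5.6 allows exclusion for lack of compliance with dosing. These controls would miss a small, silent residual. There the effect is about 2 to 5 percentage points, and no hypothesis, decision rule or recovery threshold depends on it (SAP 4.1 and 4.2).

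Two side issues change no shown result. Neither document states that post-dose [14C] is net of the pre-dose blanks, but the blanks are collected and the manuals may say so. Footnote q of the schedule of activities makes the fecal blank conditional while Protocol 8.4.3 requires it, which is a clerical mismatch.

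**Conclusion.** No change is called for. The plan states the correct denominator, foresees collection and assay of the leftovers, and delegates preparation and administration details to a technical agreement and site instructions outside the file. The missing derivation is a gap in detail. An analyst who follows the written definition would take measured [14C] prepared less measured residual, or another documented reconciliation of the delivered dose.

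A bias is possible but not shown. It needs two things together: the residual goes unmeasured, and the prepared or nominal dose is used despite the definition. Its size cannot be derived from the documents. On an assumed residual of 2% to 5%, a true 90% recovery would read 88.2% to 85.5%, with the urine-to-feces split unchanged. This conclusion assumes that the unseen documents handle the dose as the Protocol's definition implies. If they were shown to use the nominal 420 nCi, the concern would have to be reopened.

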## **6.3. Measures to Minimize Bias: Randomization and Blinding**

### **6.3.1. Allocation to Study Intervention**

The site staff will assign participant numbers to the participants as they are screened for the study. Pfizer will provide a randomization schedule to the investigator and, in accordance with the randomization numbers, the participant will receive the study treatment regimen assigned to the corresponding randomization number.

## **6.4. Study Intervention Compliance**

When participants are dosed at the site, they will receive study intervention directly from the investigator or designee, under medical supervision. The date and time of each dose administered in the clinic will be recorded in the source documents and recorded in the CRF. The dose of study intervention and study participant identification will be confirmed at the time of dosing by a member of the study site staff other than the person administering the study intervention.

The site will complete a preparation record, which may be detailed in the TA. It does not preclude the use of an existing appropriate clinical site documentation system. The existing clinical site's documentation system should capture all pertinent/required information on the preparation and administration of the dose. This may be used in place of the Preparation Record after approval from the sponsor and/or designee.

